1.4 Procedures

Participants will visit the laboratory for testing on 4 occasions. A minimum of 72-hours washout is required between visits. Before each session involving exercise (Visits 1,3,4), subjects will be asked to prepare as if each visit was a competition or important training session in their training schedule, and to ensure preparation is as similar as possible prior to each visit to minimize variability in results. This will include, but is not limited to, avoiding alcohol and strenuous exercise for 24 hours, ensuring a proper sleep the night prior, and consuming a pre-exercise meal that they are accustomed to timed appropriately prior to each visit. However, participants will be advised not to consume any ergogenic aids (i.e., sodium bicarbonate) or stimulants (i.e., significant doses of caffeine) for 24 hours prior to each visit, even if they typically utilize such strategies during competition. All visits involving exercise (Visits 1,3,4) will be performed at a similar time of day in order to avoid any diurnal variation in exercise performance (Kusumoto et al., 2021).

The first visit will involve participant consent, screening for inclusion based on a maximal exercise test, and familiarization with pulmonary function measurements. Participants will first re-read the consent form. They will be given the opportunity to ask any questions related to their involvement, then be asked to sign the informed consent. Participants will also complete a PAR-Q+ form, which will be reviewed prior to partaking any exercise in the laboratory. Participants will then be familiarized with pulmonary function testing equipment and protocols, and undergo resting spirometry and FeNO measurements (described in detail above).

Spirometry will involve maximal inspiration followed by maximal forceful expiration to determine FEV₁, FVC, FEF₂₅₋₇₅, & PEFR. FeNO will be measured by expiring into the portable device 4 times to assess lung inflammation. Following resting pulmonary function measurements, subjects will complete a 10-minute warmup at 1-watt/kilogram body weight on a Velotron DynaFit Pro cycle ergometer, before performing a step-incremental graded exercise test (GXT). The step-incremental GXT will consist of 3-minute stages, starting at 100 watts with power output increasing by 25 watts/stage, until the subject reaches volitional exhaustion, is unable to maintain 60 revolutions per minute (RPM), or is unwilling to continue. Blood lactate will be sampled via finger prick during the last 30-seconds of each stage, and subjects will be asked to rate their perceived exertion at the end of each stage. Following completion of the test, subjects will be given a brief recovery before cycling for 5-minutes at the power output 10% below their previously calculated anaerobic threshold to mimic experimental visits 3 and 4. Anaerobic threshold will measured as the work rate associated with blood lactate at 4mmol/L, indicating a change from metabolic steady state to a non-steady state attainment of VO2max. During this constant workload bout, subjects will be instructed as to how to complete an inspiratory capacity maneuver, provide rating of perceived exertion, and rate their feelings of dyspnea. Subjects will then perform post-exercise pulmonary function measures identical to that completed at rest, prior to completing a verification exercise bout (VEB) at 105% of the previously achieved maximum work rate. Subjects will be asked to cycle for as long as possible at the specified work rate until they are no longer able to maintain 60 RPM, and time-toexhaustion will be recorded. Subjects will then perform a final round of pulmonary function measures. Participants will be suited with a mouthpiece connected to a three-way non-rebreathe

valve, and expired gas and flow will be analyzed by a ParvoMedics' TrueOne 2400 metabolic measurement system (Sandy, UT, USA).

The second visit will consist of resting exposure to ozone and pulmonary function tests. Subjects will conduct pre-ozone resting spirometry, FeNO, dyspnea, and symptom measurements, followed by 2-hours of resting O₃ exposure at 750ppb. During the resting exposure, subjects will be seated with a three-way non-rebreathe valve and mouthpiece connected via tube to the ozone chamber. Nose-clips will be worn for the entirety of the protocol, and expired volumes will be analyzed to determine average minute ventilation, and effective dose of O3 (minute ventilation x O₃ concentration x exposure duration) (Silverman et al., 1976). Subjects will be permitted to use personal electronic devices (phone, laptop, tablet etc.) during exposure, provided no significant movement is required. Following exposure, subjects will complete identical spirometry, FeNO, symptoms, and dyspnea measurements immediately and 30-minutes post-exposure to that completed pre-exposure. Post-exposure and pre-exposure values will be compared to determine resting response to O3.

The third and fourth visits will consist of identical procedures, randomized as to the order of the O3 and control conditions. During both experimental trials, a lab member other than the researcher will control the O₃ concentration in order to maintain blinding of the participant and the researcher as to the condition. During the O₃ exposure, subjects will receive 170ppb O₃, and during the control exposure subjects will receive room air (typically <10ppb O₃). Upon arrival in the laboratory, the researcher will confirm that pre-visit requirements (detailed above) are met, prior to resting spirometry, FeNO, symptoms, and dyspnea measurements. Subjects will then be connected via tube and mouthpiece/valve to the O₃ chamber. While remaining connected to the O₃ chamber, participants will then complete a standardized warmup on the Velotron of 25-

Page 10 of 23

minutes at 10% below previously established aerobic threshold. Subjects will then be provided with 5-minutes of rest prior to completing 30-minutes at 10% below anaerobic threshold. Expired gas and volumes will be analyzed throughout the trial, and participants will perform an inspiratory capacity test, have blood lactate sampled via finger-prick, rate their perceived exertion and dyspnea every 10-minutes (10,20,30-minutes into exercise). Post-exercise, subjects will remove their mouthpiece and complete spirometry, FeNO, dyspnea, and symptoms testing (~5mins), prior to reattaching the mouthpiece and completing a time-to-exhaustion test at 105% of peak power achieved during the GXT. Strong verbal encouragement will be provided to subjects, and exercise will be stopped when they are no longer able to maintain 60 RPM, and time-to-exhaustion will be recorded. Post-exercise, a final set of pulmonary function, symptoms, and dyspnea testing will occur at 30-minutes following completion of the submaximal exercise bout.

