1.5 Data Analysis

As the purpose of this research study is to assess the interaction between O₃ exposure and cardiorespiratory function during rest and exercise in healthy athletes, we aim to characterise the relationship between resting response and exercise response, as well as assess the effects of ozone exposure on pulmonary function, ventilatory patterns and exercise parameters. To assess susceptibility to exercising O₃ response, a regression analysis will occur between the reduction in spirometry values post 2-hours resting exposure at 750ppb and the reduction in spirometry values post-O₃ condition exercise trial. It is hypothesized that greater decrements in FEV1, FVC, FEF₂₅₋₇₅ and PEFR will occur following exercise under O₃ exposure in subjects who also exhibited greater expiratory flow limitations following resting exposure.

Page 11 of 23

Examining ventilatory patterns during exercise is another primary objective of the proposed research study. By comparing tidal volume, breathing frequency, and inspiratory capacity throughout the constant work-rate exercise bout between the two experimental conditions through mixed models, further insight into how O₃ exposure may impact ventilation may be gained.

Analyzing time to exhaustion (in seconds) for the maximal constant work-rate exercise bouts between the two experimental conditions will also be assessed by mixed models. Potential differences between the two conditions will help elucidate whether performance changes occur due to O₃ exposure. Further analysis of ratings of perceived exertion, dyspnea, and FeNO via mixed models will also occur between the two experimental trials.

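### The preparation rules and arrival check leave out Visit 2, which supplies the predictor in the susceptibility regression; extending them is a minor, cheap improvement

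*Combined protocol and SAP*

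**What the plan says.** All of this is in the combined protocol and SAP.

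- **Preparation (section 1.4).** "Before each session involving exercise (Visits 1,3,4), subjects will be asked to prepare as if each visit was a competition". The instructions that follow cover alcohol and hard exercise in the preceding 24 hours, sleep, and a familiar meal. Their stated aim is to reduce variability.
- **Time of day (section 1.4).** "All visits involving exercise (Visits 1,3,4) will be performed at a similar time of day", and the reason given is "in order to avoid any diurnal variation in exercise performance".
- **Stimulants and ergogenic aids (section 1.4).** Athletes are told to avoid "stimulants (i.e., significant doses of caffeine) for 24 hours prior to each visit". The sentence sits inside the paragraph on exercise visits, so it may or may not reach Visit 2.
- **Spacing (section 1.4).** "A minimum of 72-hours washout is required between visits". This does include Visit 2.
- **Arrival check (section 1.4).** In the text for Visits 3 and 4, "the researcher will confirm that pre-visit requirements (detailed above) are met". The Visit 2 text has no such step.
- **Use of Visit 2 (sections 1.4 and 1.5).** "Post-exposure and pre-exposure values will be compared to determine resting response to O3". In section 1.5, "a regression analysis will occur between the reduction in spirometry values post 2-hours resting exposure at 750ppb" and the reduction after the exercise trial under ozone. This is the first analysis listed.

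**The concern.** The plan sets preparation rules to limit variability, and then stops them short of the visit that provides the explanatory variable for its first-listed analysis. The volunteers are athletes in training, so a hard session the day before Visit 2 is a realistic prospect and, as written, is allowed.

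The side of the regression matters. Random error in the outcome (the ozone trial at Visit 3 or 4) costs precision. Independent random error in the predictor costs precision and also biases the slope toward zero. If looser conditions at Visit 2 did add such error, resting susceptibility would look less closely related to the exercise response than it is. Conditions that were neither set nor recorded at Visit 2 could not be recovered afterwards.

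**Working it through.** **1. The plan's own figure.** Section 1.1 uses a 0.95 L fall in FEV1, an SD of 0.86 L, power 0.8 and alpha 0.05, and arrives at 15 subjects, raised to 24. Taken as a paired comparison with zero within-subject correlation, the SD of the difference is 0.86 × √2 = 1.216 L and the standardised effect is 0.95 / 1.216 = 0.781. The noncentral t distribution, two-sided 0.05, gives power 0.803 at n = 15, so the figure reproduces. It sizes the FEV1 crossover contrast. No power or sample size is given for the regression, and nothing in the calculation depends on Visit 2.

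**2. Which rule reaches which visit.**

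| Rule in section 1.4 | Visit 1 | Visit 2 | Visits 3 and 4 |
|---|---|---|---|
| Alcohol, hard exercise, sleep, meal | yes | no | yes |
| Similar time of day | yes | no | yes |
| Ergogenic aids, stimulants | yes | only if read literally | yes |
| 72-hour spacing | yes | yes | yes |
| Arrival check | not described | not described | yes |

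**3. What survives in a same-day change.** Write the pre-exposure reading as a + u and the post-exposure reading as a + u + c + d. Here a is the athlete's usual level, u a shift from that day's conditions, c the ozone response and d any further departure. The difference is c + d, so u cancels. A drift over the 2 hours that is the same in every athlete only moves the intercept. What is left is the part of d that varies between athletes: day-specific changes in the ozone response, or individual drift. The documents give no data on either.

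**4. Size, by illustration for FEV1.** Let s be the between-athlete SD of the resting change under standardised preparation (ordinary measurement error is already inside it), and e the SD of the error added by not standardising Visit 2, independent of everything else. The slope is multiplied by

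λ = s² / (s² + e²).

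Both s and e are assumptions.

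| e (L) | s = 0.3 L | s = 0.5 L |
|---|---|---|
| 0.05 | 0.0900 / 0.0925 = 0.97 | 0.2500 / 0.2525 = 0.99 |
| 0.10 | 0.0900 / 0.1000 = 0.90 | 0.2500 / 0.2600 = 0.96 |
| 0.15 | 0.0900 / 0.1125 = 0.80 | 0.2500 / 0.2725 = 0.92 |

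The loss is larger only if the true spread is small: with s = 0.2 L and e = 0.15 L, λ = 0.0400 / 0.0625 = 0.64.

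**5. What that would do to power.** With N = 24, the correlation becomes r√λ, and Fisher's z gives power ≈ Φ(atanh(r√λ) × √21 − 1.96). The correlations r are also assumed.

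| λ | r = 0.5 | r = 0.6 |
|---|---|---|
| 1.0 | 0.71 | 0.89 |
| 0.9 | 0.66 | 0.84 |
| 0.8 | 0.60 | 0.78 |

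**The case against.** The strongest reply is that the scope looks deliberate. Visit 2 is seated rest. The preparation text is framed around competition and exercise, and the time-of-day rule gives exercise performance as its reason. The predictor is already a same-day change, so much of what preparation might alter cancels. The documents nowhere say that prior exercise, alcohol, sleep, meals or time of day alters a resting ozone response.

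Much of this stands, and it rules out several stronger readings that a reader might infer:

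- *That the slope is diluted.* The documents show only that it could be. They give neither the added noise nor the spread of the resting response.
- *That Visit 2 is uncontrolled.* The 72-hour spacing keeps the maximal tests of Visit 1 away from it, and the stimulant rule may apply. The missing arrival check is not peculiar to Visit 2 either; none is described for Visit 1.
- *That the whole unreliability of the predictor is at stake.* Some error would remain under any preparation rule: section 1.2 itself accepts 150 mL between the two best efforts. Only the added part, e above, could be recovered.
- *That the time-of-day rule must be extended.* The regression is across athletes. Matching times within an athlete does not equalise Visit 2 times between athletes. If time of day did affect the response, matching could put a shared component into predictor and outcome and inflate the association.

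What the reply does not answer is why a stated aim of limiting variability should stop at the predictor visit. The 72-hour spacing governs laboratory visits; it does not govern training, alcohol or sleep outside them. Cancellation is also only partial. Visit 2 has no room-air counterpart, so an individual athlete's drift over the 2 hours cannot be separated from that athlete's ozone response.

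**Conclusion.** The point holds as a minor one. The preparation rules and arrival check do not reach the visit that supplies the predictor, and this could weaken the susceptibility slope. The amount is unknown. Under the assumptions in the working (independent added error of 0.05 to 0.15 L in the FEV1 change), the slope loss runs from about 1% to 8% if the between-athlete SD is 0.5 L, and from about 3% to 20% if it is 0.3 L. It may therefore be negligible. The documents do not support saying that the regression is invalid, that a null result could be put down to this, or that the sample size of 15 or 24 is affected. The case for acting is that the change is cheap and that conditions not recorded at Visit 2 cannot be reconstructed later.

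**What to change.** In section 1.4:

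- Apply the existing preparation rules (alcohol, strenuous exercise, sleep, meal) to Visit 2.
- Make the arrival check at Visit 2 as well as at Visits 3 and 4.
- State plainly that the ergogenic-aid and stimulant rule covers all four visits.
- Record the Visit 2 start time and any breach of the rules.
- Optionally, book Visit 2 at a similar time of day to the exercise visits where feasible. The recorded start time is the more useful part, since it lets time of day be examined in the regression.

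The cost is a few lines of wording, one more day of restricted training for each athlete, and slightly less flexible booking. No figure in the plan needs to be recalculated.

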Sample size was calculated using data from previous studies that examined changes in FEV1 in athletes following ozone exposure during exercise. A similar crossover design in elite athletes utilizing ozone exposure at 200ppb found a 0.95-litre reduction in FEV1 following exercise, with a standard deviation of post-exercise measures of 0.86-litres (Gong et al., 1986). Calculation for a crossover design based on analysis of variance F-tests using these values with a power of 0.8 and an alpha level of 0.05 led to a sample size of 15 subjects. Sample size will be increased to 24 to include female subjects.

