1.2 Measures/Instruments

O3 will be produced through the ACT-5000 Ozonetech corona discharge generator, (Mellifiq, Sweden), and mixed with room air in a sealed 3m x 3m x 2m chamber. O₃ will be delivered to subjects via a tube connected to the inspiratory valve on a three-way non-rebreathe mouthpiece. The Thermo ScientificTM 49iQ Ozone Analyzer (Franklin, MA, USA) will be attached to the inspiratory tube and used as an O3 sensor. Calibration will occur according to the manufacturing standards using the Thermo ScientificTM 49iQ Ozone Primary Standard generator.

Spirometry will be measured through the ParvoMedics OUS-SPIRO on the metabolic cart (Salt Lake City, UT, USA), which will be calibrated prior to each use. While wearing a nose-clip, participants will be asked to complete a maximal inspiration to maximal lung capacity followed by a maximal forceful exhalation for 6-seconds, following breathing out at the end of a normal breath. This will allow for measurement of forced expiratory volume in one-second (FEV1), forced vital capacity (FVC), forced mid-expiratory flow (FEF₂₅₋₇₅), and peak expiratory flow rate (PEFR). Based on guidelines provided by the American Thoracic Society (ATS), trials will be repeated a minimum of 3 times until the two largest FEV1 and FVC values differ by less than or equal to 150mL (Graham et al., 2019). Spirometry values will be compared between the two experimental trials to examine how O₃ exposure may impact development of expiratory flow limitation.

Fractional nitric oxide concentration in expired breath (FeNO) will be measured by a calibrated 2nd generation NOBreathe® FeNO monitor (Bedfont® Scientific Ltd., England). Participants will be instructed to perform a deep inhalation away from the mouthpiece, and exhale at a consistent flow rate for 12 seconds into the mouthpiece of the device until prompted to stop by the monitor. Four measurements will be taken at each specified time point. FeNO will be compared between the two experimental trials to examine how O₃ exposure may impact lung inflammation.

Symptoms will be measured via a custom brief questionnaire previously used in the laboratory. Before and after each exercise bout, participants will be asked to rate symptoms related to their eyes, nose, throat, chest, and general health on a 0-5 scale, where 0 means "you

Page 5 of 23

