1.3 Study Design

This research design can be characterized as a double-blind crossover with pre- and postmeasures. Ozone pollution status is the independent variable, of which there are two levels during the experimental trials: ozone exposure at 170 parts per billion (ppb) O3, and room air (<10 ppb O3). Testing will take place over four laboratory sessions, with a minimum of 72 hours of washout between each visit. During the first session, subjects will undergo a step-incremental test on a cycle ergometer to determine subject characteristics and identify anaerobic threshold, followed by familiarization of exercise pulmonary function tests. During the second visit, subjects will undergo resting spirometry and assessment of exhaled nitric oxide before and after exposure to 120 minutes of O₃ at 750ppb to characterize resting response. The third and fourth laboratory visits will consist of 30-minutes of cycling at the workload associated with 10% below previously established anaerobic threshold with exposure to either ozone or room air. Post-exercise spirometry and FeNO measures will be obtained prior to a time to exhaustion test at 105% of previously established peak power output. During the O₃ condition, subjects will be exposed to 170ppb for 60 minutes prior to, and during the cycling tasks, whereas during the control condition subjects will breathe room air for the identical procedures. Both the primary researcher and subjects will be blinded to the experimental condition for each visit, with the order randomized for each subject.

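### The time-to-exhaustion test starts when open-ended post-bout testing finishes, so rest before it can differ between the ozone and air trials

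*Combined protocol and SAP*

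**What the plan says.** Section 1.4 Procedures puts the post-bout tests between the 30-minute ride and the exhaustion test. With the mouthpiece off, subjects "complete spirometry, FeNO, dyspnea, and symptoms testing (~5mins), prior to reattaching the mouthpiece and completing a time-to-exhaustion test". Section 1.3 Study Design gives the same order: "Post-exercise spirometry and FeNO measures will be obtained prior to a time to exhaustion test at 105% of previously established peak power output". The approximate five minutes is the only timing given for this interval.

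Section 1.2 Measures/Instruments sets what has to fit into it:

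- Spirometry: "trials will be repeated a minimum of 3 times until the two largest FEV1 and FVC values differ by less than or equal to 150mL". Each effort is a "maximal forceful exhalation for 6-seconds". No maximum number of efforts or time limit is stated.
- FeNO: "Four measurements will be taken at each specified time point", and at each one the participant must "exhale at a consistent flow rate for 12 seconds into the mouthpiece".
- Dyspnea and symptom ratings, with no duration given.

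The two trials are meant to match: "The third and fourth visits will consist of identical procedures, randomized as to the order of the O3 and control conditions". Section 1.5 Data Analysis compares time to exhaustion between conditions with mixed models, to judge whether ozone changes performance. It names no covariate for the interval.

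**The concern.** The start of the exhaustion test is set by the end of a procedure whose length depends on the participant's own results. Two trials with the same procedures can therefore have different rest before the test and different time off the mouthpiece, which in the ozone trial is a break in exposure.

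The stopping rule works on FEV1 and FVC. The plan expects ozone to change these measures: Section 1.5 hypothesises decrements in both, and the sample size in Section 1.1 rests on a cited study at 200 ppb that "found a 0.95-litre reduction in FEV1 following exercise, with a standard deviation of post-exercise measures of 0.86-litres". If ozone changes how many efforts are needed, the interval becomes a second difference between the conditions. It would arise after exposure, so neither randomising the order nor blinding would remove it. If the interval varies only at random, it still adds noise to a within-person comparison, to the extent that rest affects the result.

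Time to exhaustion is the outcome from which the plan will read a performance effect, and the document gives no power calculation for it.

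**Working it through.** **Is the interval controlled anywhere?** Section 1.4 fixes two neighbouring times: the rest before the 30-minute bout (5 minutes) and the final test set (30 minutes after the submaximal bout). The start of the exhaustion test has no such anchor. Nothing in the document caps the interval, requires it to be recorded, matches it between Visits 3 and 4, or adjusts for it.

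**Inputs from the document (Section 1.2).** At least 3 spirometry efforts of 6 s each, and 4 FeNO exhalations of 12 s each. Exhalation time alone is 3 × 6 + 4 × 12 = 66 s. With 8 efforts it is 8 × 6 + 4 × 12 = 96 s. The rest of the interval is recovery between efforts, questionnaires and refitting the mouthpiece, for which the document gives no times.

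**Assumed pacing.** 30-60 s per spirometry effort including recovery, 30-60 s in each of the three gaps between four FeNO exhalations, and 30-60 s for the questionnaires. With n efforts:

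Interval (min) = n × (0.5 to 1) + 4 × 0.2 + 3 × (0.5 to 1) + (0.5 to 1)

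- n = 3: 1.5 + 0.8 + 1.5 + 0.5 = 4.3 to 3 + 0.8 + 3 + 1 = 7.8 minutes
- n = 4: 4.8 to 8.8 minutes
- n = 5: 5.3 to 9.8 minutes
- n = 8: 6.8 to 12.8 minutes

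Each further effort adds 0.5-1 minute. The plan's figure of about five minutes is reproduced at the fast end of this range with three efforts (4.3) or four (4.8).

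**Faster pacing.** With a 15 s gap after every exhalation, and leaving out questionnaires and refitting:

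- n = 3: 3 × (6 + 15) + 4 × (12 + 15) = 171 s = 2.85 minutes
- n = 8: 8 × (6 + 15) + 4 × (12 + 15) = 276 s = 4.6 minutes

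So five minutes is feasible but not guaranteed, and the interval lengthens with the number of efforts at any pace.

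**Effect on time to exhaustion.** This cannot be computed. The document gives neither a standard deviation for time to exhaustion nor a relation between recovery and performance. For scale only: with 24 participants, a paired F-test at alpha 0.05 and 80% power, an assumed standard deviation of paired differences of 15, 30 or 45 s gives a detectable difference of about 9, 18 or 27 s. Whether a minute or more of unequal rest matters on that scale is unknown.

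**The case against.** The strongest reply is that the mechanism is not in the plan. A lower FEV1 is not a less repeatable FEV1, and nothing in the document shows that ozone makes the 150 mL criterion harder to meet. There is no symptom hypothesis either; symptoms are only to be compared. This stands. A reader might infer that affected participants will need more efforts on the ozone day, rest longer, and so have a performance loss hidden. The document does not support that. Any excess of efforts is an assumption, and extra maximal manoeuvres could also tire a participant.

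Other points carry weight. The five-minute figure is a common target for both visits. Participants will have completed six spirometry sets before Visit 3: three at Visit 1, two of them after exercise, and three at Visit 2, two of them after ozone. The researcher is blinded, and the 30-minute test set limits drift. The spirometry rule cites a guideline that may set a limit on efforts, but it is not before us. FeNO is fixed at four exhalations in both trials, so by design it adds length rather than a difference between them. These points reduce the likely variation, but none makes the interval equal.

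Time to exhaustion is also not labelled primary, and the study is sized on FEV1. A remedy that cut spirometry short or moved it later could harm the outcome used for sizing. That is a good reason to leave the test order and the repeatability rule alone. It is not a reason to leave the start of the exhaustion test floating.

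**Conclusion.** The point holds in a limited form. Followed as written, the protocol lets rest and time off the mouthpiece before the exhaustion test differ between Visits 3 and 4, through a stopping rule based on measures that ozone is expected to change. The difference may be tied to condition; if it is not, it is still avoidable noise wherever rest affects performance. Under the assumed pacing the minimum set takes 4.3-7.8 minutes and each further effort adds 0.5-1 minute. Those figures rest on the stated pacing assumptions, and a faster team would be quicker. The document supports neither a direction of bias nor a size for it. The sample size calculation is not affected. This is an inexpensive design improvement, not a demonstrated bias.

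**What to change.** In Section 1.4, start the exhaustion test at one fixed time after the end of the 30-minute bout, identical in Visits 3 and 4. Choose that time from Visit 1, where spirometry and FeNO already sit between a constant-load ride and a test at 105% of maximum work rate. Allow for the symptom and dyspnea ratings, and make the interval long enough for nearly all participants to complete the full set. Keep the test order the same in both visits and leave the repeatability rule as it is.

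Record the actual interval at each visit, and examine deviations from the fixed time in a sensitivity analysis. Adjusting for the interval alone would be weaker than fixing it, because it is measured after exposure and may itself be affected by condition.

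The cost is a sentence in the protocol, a timer and one recorded time per visit. The downside is a somewhat longer pause, and so a longer break in exposure, in both trials. A few participants may still overrun, and the record will show them. The change belongs before the first Visit 3, since rest that was unequal and unrecorded cannot be recovered later.
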